| Insertion attempts     |  1  2  3  4  5  6  7  8  9  10  11  12  13  14  15  16  17  18  19  20  21  22  23  24  25  26  27  28  29  30  31  32  33  34  35  36  37  38  39  40  41  42  43  44  45  46  47  48  49  50  51  52  53  54  55  56  57  58  59  60  61  62  63  64  65  66  67  68  69  70  71  72  73  74  75  76  77  78  79  80  81  82  83  84  85  86  87  88  89  90  91  92  93  94  95  96  97  98  99  100  101  102  103  104  105  106  107  108  109  110  111  112  113  114  115  116  117  118  119  120  121  122  123  124  125  126  127  128  129  130  131  132  133  134  135  136  137  138  139  140  141  142  143  144  145  146  147  148  149  150  151  152  153  154  155  156  157  158  159  160  161  162  163  164  165  166  167  168  169  170  171  172  173  174  175  176  177  178  179  180  181  182  183  184  185  186  187  188  189  190  191  192  193  194  195  196  197  198  199  200  201  202  203  204  205  206  207  208  209  210  211  212  213  214  215  216  217  218  219  220  221  222  223  224  225  226  227  228  229  230  231  232  233  234  235  236  237  238  239  240  241  242  243  244  245  246  247  248  249  250  251  252  253  254  255  256  257  258  259  260  261  262  263  264  265  266  267  268  269  270  271  272  273  274  275  276  277  278  279  280  281  282  283  284  285  286  287  288  289  290  291  292  293  294  295  296  297  298  299  300  301  302  303  304  305  306  307  308  309  310  311  312  313  314  315  316  317  318  319  320  321  322  323  324  325  326  327  328  329  330  331  332  333  334  335  336  337  338  339  340  341  342  343  344  345  346  347  348  349  350  351  352  353  354  355  356  357  358  359  360  361  362  363  364  365  366  367  368  369  370  371  372  373  374  375  376  377  378  379  380  381  382  383  384  385  386  387  388  389  390  391  392  393  394  395  396  397  398  399  400  401  402  403  404  405  406  407  408  409  410  411  412  413  414  415  416  417  418  419  420  421  422  423  424  425  426  427  428  429  430  431  432  433  434  435  436  437  438  439  440  441  442  443  444  445  446  447  448  449  450  451  452  453  454  455  456  457  458  459  460  461  462  463  464  465  466  467  468  469  470  471  472  473  474  475  476  477  478  479  480  481  482  483  484  485  486  487  488  489  490  491  492  493  494  495  496  497  498  499  500  501  502  503  504  505  506  507  508  509  510  511  512  513  514  515  516  517  518  519  520  521  522  523  524  525  526  527  528  529  530  531  532  533  534  535  536  537  538  539  540  541  542  543  544  545  546  547  548  549  550  551  552  553  554  555  556  557  558  559  560  561  562  563  564  565  566  567  568  569  570  571  572  573  574  575  576  577  578  579  580  581  582  583  584  585  586  587  588  589  590  591  592  593  594  595  596  597  598  599  600  601  602  603  604  605  606  607  608  609  610  611  612  613  614  615  616  617  618  619  620  621  622  623  624  625  626  627  628  629  630  631  632  633  634  635  636  637  638  639  640  641  642  643  644  645  646  647  648  649  650  651  652  653  654  655  656  657  658  659  660  661  662  663  664  665  666  667  668  669  670  671  672  673  674  675  676  677  678  679  680  681  682  683  684  685  686  687  688  689  690  691  692  693  694  695  696  697  698  699  700  701  702  703  704  705  706  707  708  709  710  711  712  713  714  715  716  717  718  719  720  721  722  723  724  725  726  727  728  729  730  731  732  733  734  735  736  737  738  739  740  741  742  743  744  745  746  747  748  749  750  751  752  753  754  755  756  757  758  759  760  761  762  763  764  765  766  767  768  769  770  771  772  773  774  775  776  777  778  779  780  781  782  783  784  785  786  787  788  789  790  791  792  793  794  795  796  797  798  799  800  801  802  803  804  805  806  807  808  809  810  811  812  813  814  815  816  817  818  819  820  821  822  823  824  825  826  827  828  829  830  831  832  833  834  835  836  837  838  839  840  841  842  843  844  845  846  847  848  849  850  851  852  853  854  855  856  857  858  859  860  861  862  863  864  865  866  867  868  869  870  871  872  873  874  875  876  877  878  879  880  881  882  883  884  885  886  887  888  889  890  891  892  893  894  895  896  897  898  899  900  901  902  903  904  905  906  907  908  909  910  911  912  913  914  915  916  917  918  919  920  921  922  923  924  925  926  927  928  929  930  931  932  933  934  935  936  937  938  939  940  941  942  943  944  945  946  947  948  949  950  951  952  953  954  955  956  957  958  959  960  961  962  963  964  965  966  967  968  969  970  971  972  973  974  975  976  977  978  979  980  981  982  983  984  985  986  987  988  989  990  991  992  993  994  995  996  997  998  999  1000  1001  1002  1003  1004  1005  1006  1007  1008  1009  1010  1011  1012  1013  1014  1015  1016  1017  1018  1019  1020  1021  1022  1023  1024  1025  1026  1027  1028  1029  1030  1031  1032  1033  1034  1035  1036  1037  1038  1039  1040  1041  1042  1043  1044  1045  1046  1047  1048  1049  1050  1051  1052  1053  1054  1055  1056  1057  1058  1059  1060  1061  1062  1063  1064  1065  1066  1067  1068  1069  1070  1071  1072  1073 <input type="checkbox |

## Appendix C

### CASCADE STUDY DATA COLLECTION TOOL

| Please provide in this format: |            |             |     | Not in this format: |            |                          |     |
|--------------------------------|------------|-------------|-----|---------------------|------------|--------------------------|-----|
| MRN                            | HAR        | Medication  | ... | MRN                 | HAR        | Medication               | ... |
| 1234567                        | 2000000001 | Albuterol   | ... | 1234567             | 2000000001 | Albuterol
Simvastatin | ..  |
| 1234567                        | 2000000001 | Simvastatin | ... |                     |            |                          |     |

| Item  | Values/examples   | Description  |
|---|---|--|
| MRN   | 7 or 9 digit number   | Patient's MRN  |
| HAR   | 10 digit number   | Patient's HAR  |
| Name  | XXX, XXX alphanumeric   | Patient full name  |
| Sex   | Male/Female   | Patient's gender   |
| Age   | Number  | Patient's age at admission (number)  |
| Line, Drain, Airway, Tubes and Wound (LDAW) of the following types: CVC, PICC and PIV             | Include only the following: CVC Double Lumen, CVC Single Lumen, Peripheral IV, PICC Double Lumen, PICC single lumen, PICC Triple Lumen                                  | Specifies the type of LDAW that was placed   |
| Date of LDAW placement  | XX/XX/XXXX X:XX:XX AM/PM  | The date and time the LDAW was placed  |
| Date of LDAW removal  | XX/XX/XXXX X:XX:XX AM/PM  | The date and time the LDAW was removed   |
| Calculated field:
Duration of LDAW  | Number of hours   | This can be calculated by subtracting the LDAW placement date from the LDAW removal date. Please present results to hours.   |
| LDAW Removal Reason   | Discharge, Catheter damage, therapy complete, leaking, occluded, per order, per protocol, purulent drainage, removed by patient, infiltrated, phlebitis, site change, other (comment) | The reason that the LDAW was removed   |
| Calculated field:
Unit in which the LDAW was placed                                     | Any hospital unit name  | This unit can be determined based on the following criteria: the time of LDAW placement falls between admission into this unit AND before transferred out of or is discharged from this unit.  |
| Calculated field:
Unit in which the LDAW was removed                                    | Any hospital unit name  | This unit can be determined based on the following criteria: the time of LDAW removal falls between admission into this unit AND before the patient is transferred out of or is discharged from this unit  |
| Calculated field:
Was Cathflo (alteplase) administered during the duration of the LDAW? | Yes, No   | This can be determined based on the following criteria:
Yes if the time that during which Cathflo was administered falls within the timeframe that an LDAW was in place (i.e. after it was placed, but before it was removed)
No if the time that during which Cathflo was administered does not fall within the timeframe that an LDAW was in place (i.e. after it was placed, but before it was removed) |

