| Central Venous Catheter - CVC                        | A tunneled cuffed inserted via the internal jugular, axillary veins and the tip of the catheter is advanced into the lower one-third of the superior vena cava (SVC) at the level of the cavoatrial junction (CAJ).     | 
 
Chemotherapy and bone marrow transplant (BMT)
 
Plasmapheresis and leukapheresis
 
Intravenous (IV) antibiotic and antifungal therapy
 
Total parenteral nutrition (TPN)
 
Pain management (rarely)
 
 |
|  | A nontunneled, noncuffed inserted percutaneously into femoral, subclavian, or internal jugular vein   | -Short tem use   |
| Hemodialysis Catheter - HD                           | A cuffed tunneled central venous catheter dialysis tunneled into the superior vena cava used exclusively for hemodialysis therapy   | 
 
Hemodialysis access for acute and chronic renal failure, and end-stage renal disease (ESRD).
 
   |
| Peripherally Inserted Central Venous Catheter - PICC | Peripherally inserted central venous catheter inserted in a large peripheral vein, such as the cephalic or basilic vein, and then advanced until the tip rests in the distal superior vena cava or cavoatrial junction. | 
 
IV therapy lasting several weeks up to 6 months. 
 
TPN
 
Antibiotics
 
Analgesics
 
Repeated Blood Transfusions
 
Chemotherapy
 
 
 
                    |

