### Catheter Insertion - See Appendix B

Clinician performing insertion identified

- o Number of attempts documented
- o Radiologic confirmation

- Confirmation of catheter placement and PICC location
- Under Floroscopy

Indication for catheter-need documented

- TPN
- Intravenous fluids
- High flow infusions
  - Type of product infused
- Repeated laboratory tests
- Hemodialysis
- Medications
  - Long-term Antibiotic therapy
  - Infusion of vesicants
- Hemodynamic monitoring

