### Catheter Complication –Appendix B

#### **Mechanical Complication**

- Pneumothorax
- Air embolism
- Catheter occlusion
- Thrombosis
- Pinch-off syndrome
- Catheter malposition
- Catheter rupture

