## **CASCADE STUDY**

## **Catheter Dwell – Appendix B**

- Line insertion date
- Line insertion time
- Line removal date
- Line removal time
- Discharge Order Time for catheter removal
- Line Removal time from discharge order

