## **INCLUSION CRITERIA**

Adult patients in MICU, CCU, CSICU, SICU and hemodialysis with either CVCs, PICCs, or HD catheters.

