**Table 3- PICCs Inserted in Critical Care Units**

| PICC | 2015 | 2016 |
|-------------|-------------|-------------|
| MICU        | 32          | 10          |
| CCU         | 60          | 32          |
| CSICU       | 56          | 68          |
| SICU        | 44          | 56          |

A convenience sample of three-hundred medical records will be reviewed for this study, one-hundred and seventy-five CVCs, seventy-five PICCs, and fifty HD catheters representing 25%, 45% and 10% respectively of the total number of catheters inserted in 2016.

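### Appendix C's closed line-type list has no value for hemodialysis catheters, an eligible type with 50 of the 300 planned records, and none for triple-lumen CVCs

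*Combined protocol and SAP*

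**What the plan says.** The Data Collection Tool section refers to Appendix C for the tool's items, values and descriptions. The line-type item there is titled "Line, Drain, Airway, Tubes and Wound (LDAW) of the following types: CVC, PICC and PIV". Its value cell says that only certain values are to be included, and lists them: "CVC Double Lumen, CVC Single Lumen, Peripheral IV, PICC Double Lumen, PICC single lumen, PICC Triple Lumen". There is no catch-all value, whereas the removal-reason item in the same table does offer one.

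The body of the protocol names a different set of lines. Inclusion Criteria: "Adult patients in MICU, CCU, CSICU, SICU and hemodialysis with either CVCs, PICCs, or HD catheters". Sample Size: "one-hundred and seventy-five CVCs, seventy-five PICCs, and fifty HD catheters". Table 1 in the Introduction gives the HD catheter its own row, apart from CVC and PICC: "A cuffed tunneled central venous catheter dialysis tunneled into the superior vena cava used exclusively for hemodialysis therapy". The Appendix B form for placement and removal is headed for a triple-lumen CVC.

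**The concern.** Appendix C reads as a data request, so its list acts as a filter on which lines come back. It leaves out one eligible catheter type and admits one, the peripheral IV, that is not eligible. It also leaves out the CVC configuration named at the head of the Appendix B form.

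At stake is whether HD lines can be recognised in the extract at all. This bears on adherence. The Methodology section lists two dialysis-specific policies, D-2 and R-98, among the standards for evaluating practice. Policy C-10A, for central venous catheter maintenance, states that it does not cover dialysis catheters except through its Appendix I. A dialysis line labelled as a CVC could therefore be assessed against the wrong policy, and the primary endpoint counts outcomes by adherence. For CVCs, the extract would describe only single- and double-lumen lines.

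**Working it through.** **Planned records.** The quotas in Sample Size add up to the stated total: 175 + 75 + 50 = 300. The HD share is 50/300 = 16.7%. The plan gives no alpha, power or effect size, and the point depends on none of them.

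**Allowed values against the lines the documents name.** The list holds 2 CVC + 3 PICC + 1 peripheral IV = 6 values.

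| Line | Where it is named | Values in the list |
|---|---|---|
| CVC, single or double lumen | Inclusion Criteria and Sample Size (as CVC) | 2 |
| CVC, triple lumen | Heading of the Appendix B form | 0 |
| PICC | Inclusion Criteria and Sample Size | 3 |
| HD catheter | Inclusion Criteria, Sample Size, Table 1 | 0 |
| Peripheral IV | Not an eligible type | 1 |

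**What happens to an HD line.** The documents do not say how EPIC labels dialysis lines, so there are two cases.

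1. EPIC uses a type that is not on the list. The filter removes the line.
2. EPIC records it as a double-lumen CVC. This is plausible: Table 1 calls the HD catheter a central venous catheter, and R-98 describes the dialysis catheter as having two lumens. The line is returned, but this item cannot tell it from a CVC.

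In neither case does the item identify an HD line.

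**Which data are exposed.** Seven Appendix C fields describe the line row.

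| Field | Other stated source |
|---|---|
| Placement date and time | Catheter Dwell list |
| Removal date and time | Catheter Dwell list |
| Duration | Difference of the two above |
| Unit of placement | Catheter Management and Care list |
| Removal reason | None legible |
| Unit of removal | None legible |
| Cathflo given while the line was in place | None legible |

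So 7 − 4 = 3 fields have no other legible source. Appendix B is partly unreadable in the text available, so these three cannot be declared absent from it.

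**Triple-lumen CVCs.** Tables 2 and 3 and the quotas give no lumen counts. The share of the 175 CVC records affected cannot be computed.

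**The case against.** The strongest reply is that Appendix C is only one source. The Methodology section plans abstraction from notes, flow sheets and other records, and Data Management names EPIC, the Business Intelligence Department and clinician notes. The headings "Catheter Complication –Appendix B" and "Catheter Dwell – Appendix B" point to the other form. Nothing says that the 300 records are drawn from the Appendix C extract. HD status may also be known at selection, since hemodialysis is an inclusion setting with its own quota. The item "Indication for catheter-need documented" lists hemodialysis among its options.

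Much of this stands. It limits the consequence to the extract and makes it conditional on EPIC labelling. It does not remove the inconsistency: no section states how HD lines are to be recognised in the extract. A documented indication can label only rows that were returned, and only where it was recorded. The Limitations section itself expects incomplete documentation.

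A reader might infer more than the documents support:

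- *That HD is a comparison group.* It is an eligible type with a quota. The groups in Primary Endpoints are adherent and non-adherent care, each covering all three catheter types, and no HD-versus-CVC comparison is specified. Mislabelling reaches the comparison only indirectly, through the policy applied.
- *That 50 records or all seven fields would be lost.* The first is a quota; four of the seven fields have another stated source.
- *That the list should match C-10A.* That policy is a nursing document which also names pulmonary artery catheters and ports. It does not define the study population. The triple-lumen point rests on the Appendix B heading.

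**Conclusion.** The inconsistency is certain on the text: 0 of 6 values name an HD catheter and 0 of 6 a triple-lumen CVC, under an instruction that closes the list. The row and the Appendix B heading are both legible, so this is not an effect of text extraction.

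The consequence is narrower and less certain. It assumes that the pull is run as written, and its form depends on EPIC labelling: HD lines are either missing from this extract or merged with CVCs. It falls mainly on removal reason, unit of removal and Cathflo use for a type holding 16.7% of planned records. For CVCs the extract would be restricted by lumen count to an unknown extent. It should be corrected before the pull, but it does not show that HD data are unobtainable or that the primary comparison fails.

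**What to change.** Before the pull, add the dialysis (HD) catheter type and the triple-lumen CVC to the title and list of the line-type item, so that Appendix C agrees with Inclusion Criteria, Sample Size and the Appendix B form.

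Confirm how EPIC labels dialysis lines. If it has no separate type, flag HD lines from the hemodialysis record selection or from the documented hemodialysis indication in the chart review already planned. Link them to the extract on MRN, HAR and placement date and time, and report how many were identified that way.

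The cost is one edited row in the data request, plus some linkage work if EPIC has no separate dialysis type.

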## BACKGROUND AND SIGNIFICANCE

Central lines have no absolute placement contraindications. They afford a readily available vascular pathway for life-sustaining intravenous fluids, nutrition and medications,

repeated laboratory tests, high-flow infusions, hemodialysis, and hemodynamic monitoring that cannot be precisely measured via non-invasive means. A major factor in the choice of a central access is the intended need. A non-tunneled catheter is the best option for short-term use (days to weeks), PICCs for intermediate use (weeks to months), and tunneled CVCs for long-term care (months to years). At times when vesicant and vasoactive medications are required to avoid local tissue injury or when needed for extracorporeal therapies, central access becomes the only viable alternative. Central lines are categorized as either inserted centrally or peripherally inserted. PICC has become increasingly popular because they are easy to insert, is considered cost-effective, and has been perceived to be safe in comparison to CVCs. PICCs, however, is not without complications. Some of these complications include catheter fracture, leakage, infection, superficial and deep vein thrombosis (DVT). As with all invasive procedures, catheter-use has high probabilities for complications. With more than five million catheters inserted annually, the vulnerability of CVCs to complications mandates a careful, structured investigation from the time of insertion, during dwell time, and at removal. Central venous catheters, now commonplace in critical care, hemodialysis, and long-term care setting, requires specialized knowledge in care, management, maintenance, and documentation. Practitioners, care providers, manufacturers, and regulatory agencies have long recognized that central lines are problem prone. Mechanical, thrombotic, and infectious complications remain the leading cause of catheter malfunction and failure. The hydrophobic surface of CVCs promotes adsorption of protein and cellular adhesions, making them susceptible to thrombotic occlusion and fibrin sheath formation in as early as twenty-four hours after placement. These building blocks eventually precipitate obstruction, a frequent complication of central lines.

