### Purpose:

To outline the nursing management of patients with central venous access devices (CVAD) including but not limited to triple lumen catheters, pulmonary artery catheters and Port- a caths. (This protocol does not address management of PICC lines, Implanted Venous Devices or dialysis catheters except for information on Appendix I.)

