### Policy Statement

[figure not shown]
RNs who are validated for care and maintenance of a central venous catheter can use a dialysis catheter for IV access, and blood draw after an order is placed in the electronic medical record (EMR) by a Nephrologist.

RNs may change dressing without MD order if soiled or non-occlusive.

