#### Operational Definitions

#### Policy Statement

The appropriate flushing technique will be performed to both the arterial and venous ports of a central catheter to ensure patency. The central venous catheter is a dual lumen, radiopaque catheter with luer lock adapter used for short or long term dialysis depending on which type catheter is placed.

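### The line-type field records neither tunneled status nor HD catheters, and Table 1's HD definition is narrower than the policies used to judge adherence, so line grouping is ambiguous and may confound the CVC comparison

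*Combined protocol and SAP*

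**What the plan says.** **How lines are typed.** The line-type item in Appendix C is headed "Include only the following" and gives six values: "CVC Double Lumen, CVC Single Lumen, Peripheral IV, PICC Double Lumen, PICC single lumen, PICC Triple Lumen". CVCs are divided by lumen count only, and no value is an HD catheter. The Sample Size section plans 175 CVCs, 75 PICCs and 50 HD catheters.

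**What tunneling means in the protocol.** Background and Significance chooses the device by intended need. At one end, "A non-tunneled catheter is the best option for short-term use (days to weeks"; at the other, "tunneled CVCs for long-term care (months to years"; PICCs lie between. Table 1 has a tunneled row and a non-tunneled row, both under CVC.

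**What counts as an HD catheter.** Table 1 defines it as "A cuffed tunneled central venous catheter dialysis tunneled into the superior vena cava used exclusively for hemodialysis therapy". The Methodology section lists policies D-2 and R-98 among the adherence standards. D-2 defines a dialysis catheter by large bore and purpose, with no mention of a cuff or tunnel, and says that validated nurses "can use a dialysis catheter for IV access, and blood draw after an order is placed". R-98 describes a dual-lumen catheter "used for short or long term dialysis depending on which type catheter is placed". The general CVC policy, C-10A, states "This protocol does not address management of PICC lines, Implanted Venous Devices or dialysis catheters", apart from information in one of its appendices.

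**Analysis.** The primary endpoint counts complications in adherent and non-adherent groups. The Data Analysis section names Pearson correlation and unadjusted two-group or several-group tests. It mentions no stratification by catheter type, subtype or dwell.

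**The concern.** The protocol treats tunneling as a main divide in how a line is meant to be used, then leaves it out of the field that types the line. The single CVC quota can therefore hold lines from both ends of the protocol's own duration scale. If the two kinds differ in complication risk and also in how often care is documented as adherent, an unadjusted comparison of adherent with non-adherent CVCs mixes the effect of adherence with the effect of subtype.

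The HD group has a separate problem. The closed list cannot identify an HD catheter, and the definition in Table 1 does not match the policies by which dialysis lines would be judged. Two abstractors could file the same short-term dialysis line differently. That choice changes which group the line is counted in, and could change which policy decides whether its care was adherent.

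**Working it through.** **1. The plan's own figures.** The documents give no tunneled share, power calculation or effect size. The only figures on grouping are the sample percentages.
- CVC: 176 + 160 + 80 + 192 = 608 in 2016, and 175/608 = 28.8%, against a stated 25%.
- PICC: 10 + 32 + 68 + 56 = 166, and 75/166 = 45.2%, which agrees with the stated 45%.
- HD: no count is tabulated. The stated 10% implies 50/0.10 = 500 catheters, which cannot be checked. It is not stated which HD definition that count used.

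The CVC mismatch does not affect this point.

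**2. Where a short-term dialysis line can go.**
- Under D-2 it is a dialysis catheter, so it can be filed as HD.
- Under Table 1, if it is not tunneled, it fails the HD definition and fits the non-tunneled CVC row. Because R-98 describes a dual-lumen device, it can be recorded as a double-lumen CVC.
- If it is regarded as HD but searched for through the Appendix C list, no value retrieves it and it can be missed.

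The Inclusion Criteria cover critical care and hemodialysis adults, so such lines are not excluded. The step from short-term to non-tunneled is an inference from Background and Significance; R-98 does not use the word.

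**3. Size of confounding within CVC (illustration; all inputs assumed).** Take 175 CVCs with no effect of adherence in either subtype. Complication risk is 20% tunneled and 5% non-tunneled; adherence is 40% and 70%. Events in a group = tunneled n × 0.20 + non-tunneled n × 0.05. OR = (adherent events/non-events) ÷ (non-adherent events/non-events).

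| Tunneled share | Adherent | Non-adherent | OR |
|---|---|---|---|
| 20% (35 of 175) | 14 × 0.20 + 98 × 0.05 = 7.7 of 112 (6.9%) | 21 × 0.20 + 42 × 0.05 = 6.3 of 63 (10.0%) | (7.7/104.3)/(6.3/56.7) = 0.66 |
| 10% (17.5) | 7 × 0.20 + 110.25 × 0.05 = 6.91 of 117.25 (5.9%) | 10.5 × 0.20 + 47.25 × 0.05 = 4.46 of 57.75 (7.7%) | 0.75 |
| 5% (8.75) | 3.5 × 0.20 + 116.375 × 0.05 = 6.52 of 119.875 (5.4%) | 5.25 × 0.20 + 49.875 × 0.05 = 3.54 of 55.125 (6.4%) | 0.84 |
| Any, equal adherence | same mix in both groups | same mix in both groups | 1.0 |

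The sign is not known either. Exchanging the adherence rates at a 20% share gives 24.5 × 0.20 + 56 × 0.05 = 7.7 of 80.5 against 10.5 × 0.20 + 84 × 0.05 = 6.3 of 94.5, so OR = (7.7/72.8)/(6.3/88.2) = 1.48.

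**4. A second illustration through dwell alone.** Background and Significance gives occlusion of 14% to 36% within one to two years. Assume a constant hazard, the same for both kinds of line, with dwell of 7 to 14 days non-tunneled and 90 to 365 days tunneled. Risk = 1 − exp(−hazard × days), which gives 0.14% to 1.7% non-tunneled and 1.8% to 36% tunneled. With tunneled shares of 20% and 40% in the two adherence groups and no true effect, crude risks differ by 0.3 to 6.9 points (risk ratio about 1.7 to 1.8). With shares of 10% and 20% they differ by 0.2 to 3.4 points (about 1.5 to 1.7). Equal shares give no difference. Here the whole artefact is exposure time.

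**The case against.** **Tunneled CVCs may be few.** Table 2 counts lines inserted in critical care units, and oncology patients are excluded, while chemotherapy and bone marrow transplant head Table 1's tunneled indications. This stands: at small shares the bias shrinks, and with equal adherence it vanishes.

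**Part of the information may be recoverable.** Dwell is collected in hours, clinician notes are reviewed, and Appendix B is too damaged in the available text to show whether it has a tunneled field. HD lines might also be found outside the Appendix C list. This stands as mitigation, but no rule says that dwell or notes will be used to separate subtypes.

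**Stronger readings that the documents do not support.** A reader might infer that temporary dialysis lines will be scored against C-10A, the wrong policy. No section sorts lines by Table 1 or maps line types to policies, D-2 and R-98 are themselves listed standards, and R-98 refers to C-10A for weekly connector cap changes. Misscoring is possible, not documented. A reader might also infer that a tunneled HD line is excluded once it is used for IV access. That over-reads a definition in the Introduction that the eligibility criteria do not cite. Nor do the documents show that complications differ more within CVC than between device types: they give no rates by tunneling, the durations describe intended use, and Table 1 itself gives no such durations for CVCs.

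**The point is second-order.** No stratification by device is planned at all, and the study is exploratory. This is fair, but adding CVC/PICC/HD strata later would not separate subtypes that were never recorded.

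**Conclusion.** Two gaps are established from the text: a closed line-type list with neither tunneled status nor an HD value, and an HD definition narrower than two of the adherence standards. Ambiguous filing, and an unclear comparison policy, follow for short-term dialysis lines.

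Confounding within CVC is conditional. It needs tunneled status to be related to both adherence and complications, and the documents give neither relation and no tunneled share. Under the stated assumptions the spurious odds ratio runs from 0.66 to 1.0, and above 1 if adherence is higher in tunneled lines. These figures show what the omission could do; they do not estimate bias in this study. The point is worth acting on because the remedy is cheap before abstraction and would mean reopening charts afterwards.

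**What to change.** Before abstraction starts:

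1. Add an HD catheter value to the Appendix C line-type item, and a tunneled yes/no field for CVC and HD lines taken from the insertion note. While the list is open, check the missing triple-lumen CVC value, since the Appendix B form is headed with that device.
2. Reconcile Table 1's HD definition with D-2 and R-98 for study classification only, so that every dialysis line has one defined group. This does not bear on how any line should be used clinically.
3. State which listed policy each line type and subtype is scored against.
4. Report complications and adherence by subtype, and stratify the adherence comparison by it.

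The cost is one or two more abstracted fields across 300 records and some rewording. The downside is smaller cells: if tunneled CVCs prove rare, that stratum can only be described, but the reader will then know that it was rare.
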